• CNC word recognition score >30% (tested in subject's everyday listening				
condition for that ear)				
Previous experience with a cochlear implant				
Cochlear malformation or obstruction (i.e. ossification) that would				
preclude full insertion of electrode array in the ear to be implanted				
 Medical or psychological conditions that contraindicate surgery or impact 				
the ability to manage an implanted device or the study related procedures				
as determined by the investigator				
 Diagnosis of auditory neuropathy/dys-synchrony in either the ear to be 				
implanted or the contralateral ear				
Active middle-ear disease/infection in the ear to be implanted				
•				
Unrealistic expectations regarding potential benefits, risks and limitations inherent to implant surgical procedures as determined by the investigator.				
inherent to implant surgical procedures as determined by the investigator				
Unwillingness or inability of subject to comply with all investigational				
requirements as determined by the investigator				
Implanted Ear Only:				
CNC word scores at 12 months post implantation compared to				
preimplant word scores				
Contralateral (Non-Implanted Ear) Only:				
Unaided audiometric thresholds at 12 months post implantation test				
interval compared to preimplant				
Bilateral Listening Condition [‡] (Both Ears – Everyday Listening Condition for				
each ear):				
AzBio sentence scores in noise at 12 months postimplantation				
compared to preimplant bilateral sentence scores				
Lateralization ability at 12 months postoperative intervals compared				
to preimplantation				
Quality of life/Subjective Hearing Benefit:				
Speech, Spatial, and Qualities of Hearing (SSQ) scale at 12 months				
compared to preimplant SSQ score				
Secondary quality of life/subjective benefit endpoints include the				
Glasgow Benefit Inventory; Tinnitus Handicap Inventory and Sponsor				
developed patient report scales at 12 months postimplantation				
compared to preimplantation				
[‡] Refer to Glossary for Definitions of Bilateral Listening Condition and Everyday Listening				
Condition used within this investigational plan.				
Adverse events (AEs) will be tracked and reported according to the				
requirements of an IDE investigation until the study is closed. The number				
and percent of all subjects experiencing adverse events will be summarized by				
type and frequency of event. The AEs will be recorded and tracked between				

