Emerging research and scientific literature available to date suggests that cochlear implant is superior to current available conventional amplification options for patients with single-sided deafness or asymmetrical hearing loss after careful preoperative audiological diagnostic screening and patient selection. This is largely based on the possibility of restoring binaural hearing sensitivity with a cochlear implant. Vermeire and Van de Heyning in 2009 published one of the first studies reporting auditory outcomes of cochlear implantation in single-sided deafness (N=20 patients). Results from this study demonstrated that asymmetrically deaf patients benefited significantly in speech understanding outcomes and secondarily tinnitus suppression. Significant benefits of tinnitus abatement have been reported by various research groups and documented in peer-reviewed literature (Amoodi et al., 2011; Van de Heyning et al., 2008; Punte et al., 2011; Miyamoto et al., 1997; Battmer et al., 1989; Vermeire et al., 2009) and represents another potential advantage of electrical stimulation over conventional devices (i.e. CROS or osseointegrated options) in the treatment of patients with asymmetrical hearing loss and/or single-sided deafness.

Current research supports these initial published results and show that cochlear implantation in this clinical population is significant in helping patients improve *binaural* hearing abilities and processes, particularly speech perception enhancement in noise, sound localization and is beneficial in the reduction a number of situations in which the unilateral hearing loss was significantly problematic without this treatment (Arndt et al., 2011a; Firszt et al., 2012a,b; Vermeire and Van de Heyning, 2009; Buechner et al., 2010; Hassepass et al., 2013; Távora-Vieira et al., 2013; Blasco and Redleaf, 2014; Tokita et al., 2014; Vlastarakos et al., 2014). Lastly and importantly, current research and clinical studies have also demonstrated that cochlear implantation has had a significant qualitative improvement and impact on the perceived benefit, device acceptance and enjoyment of life (Arndt et al., 2011; Roland et al., 2011; Stelzig et al., 2011; Dwyer et al., 2014) for patients with unilateral deafness.

Although an asymmetric hearing loss of a severe-to-profound degree in one ear with much better hearing on the opposite ear (unilateral deafness/single-sided deafness) indication is not

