The SSQ (Gatehouse and Noble, 2004; Noble and Gatehouse 2006) will be used as a subjective, self-reported assessment of hearing status and hearing capability in everyday life prior to and during the feasibility study. The questionnaire is designed to measure self-reported auditory disability across a wide variety of domains to include: hearing speech in a variety of competing contexts; directional, distance and movement components of spatial hearing; segregation of sounds and attending to simultaneous speech streams; ease of listening; naturalness; clarity and identifiability of different speakers and music. The current standard versions of SSQ (5.6) and SSQ-B (5.6) will be used in the study.

Glasgow Benefit Inventory (GBI)

The GBI (Robinson, Gatehouse and Browning, 1996) is a subjective, postintervention questionnaire developed specifically to evaluate any otorhinolaryngological (ORL) interventions. Patient benefit is the change in health status resulting from the intervention. The GBI will be administered postoperatively.

Tinnitus Handicap Inventory (THI)

The THI (Newman, Jacobson and Spitzer, 1996) will be used as a subjective, self-reported measure to quantify the impact of tinnitus on daily living. The questionnaire will be administered pre and postoperatively only if the participant reports tinnitus.

Additional Metrics:

Sponsor developed patient-report subjective questionnaire/scales such as sound quality and/or quality of life related aspects may additionally be administered at various study intervals during the feasibility study only to obtain further relevant input from patients

with this clinical hearing profile receiving this type of treatment. The study intervals are identified within the study protocol when Sponsor developed subjective assessments are to be used.

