Using AzBio Sentence Test in Quiet - One list presented at 40 dBA in soundfield in the
participant's bilateral, everyday listening condition. The participant is asked to identify if
the sentence was detected from the left or right speaker. The sentence delivery from
right or left speaker is randomized.

Note: Participants may or may not be aided in one or both ears thus, testing may be aided or unaided or a combination during test administration). The test setup is as follows:

• Participant will be centered and faced forward between a right and left speaker (each positioned in corners of the audiometric suite at 45° respectively)

Self-Assessment Questionnaire(s):

- Speech, Spatial and Sound Qualities (SSQ) Questionnaire standard version (Version 5.6)
- Tinnitus Handicap Inventory (THI) Administered only if participant has reported tinnitus
- Sponsor developed patient report questionnaire/scale

Implant Surgery:

Conducted at participant's managing hearing care clinical center. Note: Implant surgery to be completed within 26 weeks of the Baseline Visit. If the surgery date exceeds this time frame, Baseline measures including audiometric and speech perception testing will need to be reevaluated.

Initial Device Activation/Fitting:

Device activation should occur within 3 to 6 weeks postimplant surgery.

Device Programming – Sound Processor Fitting: Specific Instruction:

 Study participants are to be provided with a standard everyday program with the following FDA approved signal processing strategy(ies):

HiRes™ Optima with ClearVoice

Additional programs and parameter settings are deferred to the guidance and recommendations of the participant's managing hearing care specialist.

Audiometric Testing:

- Unaided air-conduction thresholds using insert earphones at 250, 500, 1000, 2000, 4000 and 8000 Hz; unilateral, each ear. Clinical masking as appropriate.
- Unaided bone-conduction hearing thresholds at 500, 1000, 2000 and 4000 Hz;
 unilateral, each ear

Adverse Event Assessment:

An adverse event assessment is completed by the investigator at each test interval. An assessment will be completed additionally if an adverse event has occurred outside of the scheduled study test intervals (i.e. unscheduled visit).

3 and 6 Month Postimplant Test Intervals:

The three and six month post-device activation visits to occur within 12 and 24 weeks respectively (+/- 14 days) of the participant's device activation date.

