The twelve month post-device activation visit to occur within 48 weeks (+/-14 days) of the participant's device activation date.

Important Note: The participant is to be tested at each scheduled study test interval using the standard everyday program ().

Please confirm that this program is selected prior to testing.

Audiometric Testing:

- Unaided air-conduction thresholds using insert earphones at 250, 500, 1000, 2000, 4000 and 8000 Hz; unilateral each ear. Clinical masking as appropriate.
- Unaided bone-conduction hearing thresholds at 500, 1000, 2000, and 4000 Hz;
 each ear.

Speech Perception Testing:

• CNC Word Test in Quiet - Two lists of 50 words presented at 60 dBA in the *implanted* ear only

- AzBio Sentence Test in Noise Two lists presented in the following soundfield conditions at 60 dBA with a +5 dB SNR using speech-spectrum noise in the participant's everyday, bilateral listening condition. The following test conditions are to be conducted:
 - Speech Front, Noise Front (Target and Noise 0° azimuth)
 - Speech Front (0° azimuth), Noise directed to the implanted ear (90° or 270° azimuth)
 - Speech Front (0° azimuth), Noise directed to the non-implanted ear (90° or 270° azimuth)

Lateralization Testing:

AzBio Sentence Test in Quiet - One list presented at 40 dBA in soundfield in the
participant's bilateral, everyday listening condition. The participant is asked to identify if
the sentence was detected from the left or right speaker. The sentence delivery from
right or left speaker is randomized.

Note: Participants may or may not be aided in one or both ears thus, testing may be aided or unaided or a combination during test administration. The test setup is as follows:

• Participant will be centered and faced forward between a right and left speaker (each positioned in corners of the audiometric suite at 45° respectively)

Self-Assessment Questionnaire(s):

- Important Note: The Speech, Spatial and Sound Qualities Questionnaire standard SSQ version (5.6) is administered at this test interval.
- The Tinnitus Handicap Inventory (THI) Administered only if participant has reported tinnitus
- Glasgow Benefit Inventory
- Sponsor developed patient report questionnaire/scale

Adverse Event Assessment:

An adverse event assessment is completed by the investigator at each test interval. An assessment will be completed additionally if an adverse event has occurred outside of the scheduled study test intervals (i.e. unscheduled visit).

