- 5. The Speech, Spatial Qualities (SSQ) questionnaire score comparison pre-to-post device activation will be conducted to provide a subjective measure of patient perceived hearing performance/auditory benefit with this combined technology. The SSQ will aid in providing a measure of subjective perceived benefit in the restoration of binaural auditory input. SSQ scores at 12 months postimplant will be compared to the preimplant scores. Individual and group comparisons will be conducted.
- 6. Additional subjective outcome scales may also be assessed and evaluated to understand if restoration of binaural auditory input results in improvement of quality of life. This will include the Tinnitus Handicap Inventory and Sponsor developed subjective scales.

The results of the efficacy measures are expected to be generalizable to the Medicare beneficiary population. It has been shown that elderly patients can benefit from cochlear

implantation and age is not considered a limitation for cochlear implant surgery (Otol Neurotol. 2016 Jan;37(1):46-51. Outcomes After Cochlear Implantation in the Very Elderly. Wong DJ1, Moran M, O'Leary SJ.). The findings of several studies suggest that cochlear implantation can be equally effective in improving speech recognition in older patients as compared to younger adults (Schwab, B., Gandolfi, M., Lai, E., Reilly, E., Singer, L. and Kim, A.H. (2015) The Impact of Age on Cochlear Implant Performance. International Journal of Otolaryngology and Head & Neck Surgery, 4, 329-337., Zwolan, T.A., Henion, K., Segel, P., Runge, C. (2014). The role of age on cochlear implant performance, use, and health utility: a multicenter clinical trial. Otol Neurotol. 35(9):1560-8; Otol Neurotol. 2017 Jan;38(1):54-59. Cochlear Implantation in the Elderly: Does Age Matter? Rohloff K1, Koopmann M, Wei D, Rudack C, Savvas E.; Rev Laryngol Otol Rhinol (Bord). 2013;134(3):119-24. Cochlear implantation in older patients: outcomes and comparisons. Rafferty A, Tapper L, Strachan D, Raine C.)

Efficacy results will be published on clinicaltrials.gov within one (1) year of the completion date of the study.

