12.1 Adverse Event Reporting and Assessment

An adverse event (AE) is defined as any undesirable clinical occurrence experienced by a study subject when using the HiResolution System or when undergoing research procedures, whether or not the AE is considered to be device-related. The definition of an AE also includes any event related to any study procedures or to any underlying medical condition present at baseline that increases in severity during the study. An underlying medical condition that was present at the time of enrollment will not be reported as an AE, but any increase in severity during the study will be reported as an AE.

All device-related and non-device-related adverse events (AEs) will be tracked and reported accordingly throughout the feasibility study as defined above in the investigational plan and in accordance with requirements of an IDE investigation. The AEs will be recorded and tracked between completion of the informed consent form (signed and dated) and two weeks after the participant's last study visit. The number and percent of all subjects experiencing adverse events will be summarized by type and frequency of event. Adverse Events will be recorded and will include but are not limited to the following information [refer to Appendix A for Case Report Forms (CRFs)]:

The following risks associated with surgery and/or cochlear implantation are identified as anticipated Adverse Events:

- General risks
 - General anesthesia
 - Postoperative pain
 - Bleeding or infection
 - Possibility of damage to the facial nerve
 - Balance related issues (i.e. dizziness, vertigo)
 - Numbness
 - Swelling or discomfort around the ear
 - Taste disturbance
 - Increased ringing in the ears (tinnitus)
 - Neck pain
 - Skin reaction
 - Leakage of inner ear fluid or cerebrospinal fluid which may increase the risk of meningitis. Meningitis is an infection in the fluid and tissue that surround the brain and spinal cord. There are two types viral and bacterial meningitis; bacterial being the most serious type and has been reported in cochlear implant recipients. The Centers for Disease Control (CDC) recommends for patients pursuing cochlear implantation to be up to date on age-appropriate pneumococcal vaccination. More information about the CDC recommendations can be found at http://www.cdc.gov or by calling [name]. It is recommended to discuss vaccinations and surgical risks with the subjects prior to the scheduled procedure.

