 - Hearing may sound different when the cochlear implant is turned on
 - Insertion of a cochlear implant electrode will likely result in the loss of any residual hearing in the implanted ear.
- Risks associated with implantation of the internal cochlear implant device and electrode array
 - The presence of a foreign body (implant) may result in irritation
 - Redness or breakdown of the skin in the area around the implant receiver/stimulator and/or rejection of the device
 - The electrode array may migrate partially resulting in reduced hearing ability
 - Misplacement of the electrode array may result in non-auditory sensations which may require additional medical treatment, surgery and/or removal of the device, however, this is considered a rare circumstance
 - Electrical stimulation may increase tinnitus, facial nerve stimulation, balance related issues (i.e. dizziness, vertigo) or pain
 - Implantation in the cochlear may preclude the use of future implant technology

- Device failure of operation that may perhaps require removal of the device
- A risk of additional loss natural hearing as a factor of chronological age (i.e. presbycusis) and/or etiology of the hearing loss may be experienced
- Any study participant experiencing a shift in audiometric threshold of 30 dB or greater pure tone average threshold shift across 250-1000 Hz from baseline to post-operative visits will be reported as an anticipated Adverse Event under this feasibility study.
- Risks specifically associated with the clinical population evaluated in this feasibility study, that of single-sided deafness/asymmetrical hearing loss

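### A participant whose tinnitus starts after implantation has no preimplant Tinnitus Handicap Inventory score and cannot enter the planned 12-month comparison

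*Combined protocol and SAP*

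**What the plan says.** The Protocol Synopsis names the secondary subjective endpoints as "Glasgow Benefit Inventory; Tinnitus Handicap Inventory and Sponsor" developed scales, comparing 12 months with preimplantation. Section 11.0, item 6, covers additional subjective scales that may be assessed for quality of life and adds: "This will include the Tinnitus Handicap Inventory and Sponsor developed subjective scales". Item 6 gives no time point, so the timing comes from the Synopsis.

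Section 8.3.3 sets the rule for giving the THI: "The questionnaire will be administered pre and postoperatively only if the participant reports tinnitus". Section 9.0 repeats the condition at baseline, at 3 and 6 months and at 12 months, in slightly different words: "Administered only if participant has reported tinnitus". The footnote to the table in section 9.1 withholds the THI from participants who report no tinnitus before or after surgery.

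Tinnitus can move in either direction. Section 4.0 cites earlier work in which implanted patients "benefited significantly in speech understanding outcomes and secondarily tinnitus suppression". Section 12.1 lists increased tinnitus among the general risks and, for the implanted device, states that "Electrical stimulation may increase tinnitus".

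**The concern.** Whether a participant has a pair of THI scores depends on tinnitus status, which is what the THI comparison is about. Someone free of tinnitus at baseline can only stay the same or get worse, and those who get worse have no preimplant score. Someone with tinnitus at baseline can improve, and is in the comparison. A summary of the available pairs would include improvements and omit one kind of deterioration, in an item meant to show whether restored binaural input improves quality of life. With up to 15 participants (section 10.0; section 7.3 says up to 20), one or two such cases can change the picture.

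The plan also promises little that would reveal the omission. Items 1 to 5 of section 11.0 each mention individual and group comparison, and item 6 does not. The minimum individual tabulation in section 10.0 covers audiometric and speech outcomes, not questionnaires.

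**Working it through.** The plan states no THI figure, so there is nothing to reproduce. The check is to follow the rule for each tinnitus history.

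| Before implant | At 12 months | Preimplant THI | 12-month THI | Pair |
|---|---|---|---|---|
| Present | Present | Yes | Yes | Yes |
| Present | Absent | Yes | Depends on reading | Depends on reading |
| Absent | Present | No | Yes | No |
| Absent | Absent | No | No | No |

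1. **New onset (third row).** The baseline instruction in section 9.0 withholds the THI, because later onset cannot be known at that visit. This holds however the rule is read.
2. **Resolved (second row).** Section 9.0 speaks of a participant who has reported tinnitus, which most naturally keeps someone with baseline tinnitus in at 12 months. Only the present tense in section 8.3.3 allows a visit-by-visit reading, under which the 12-month score would be missing.

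**Direction.** Let N participants have baseline tinnitus, with mean THI change M. Let n new-onset cases have mean 12-month score s, and count no tinnitus as 0.

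- Mean change, all with tinnitus at either time: A = (N·M + n·s)/(N + n)
- Mean change, baseline cases only (the has-reported reading): M
- Difference: M − A = n(M − s)/(N + n)

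The difference is zero if n = 0. If n > 0 it is negative, meaning improvement is overstated, unless baseline cases worsen on average by at least s.

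**Illustration. Every input is assumed; none is in the documents.** N = 10 of 15. Persistent cases change by p = −15. The r resolved cases go from b = 50 to 0. New-onset cases go from 0 to s = 30. Then M = [(10 − r)p − r·b]/10, and the visit-by-visit reading gives p.

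| r | n | A, all with tinnitus | M, has reported | p, visit by visit |
|---|---|---|---|---|
| 0 | 0 | −15.0 | −15.0 | −15.0 |
| 0 | 2 | (−150 + 60)/12 = −7.5 | −15.0 | −15.0 |
| 2 | 1 | (−120 − 100 + 30)/11 = −17.3 | −22.0 | −15.0 |
| 2 | 2 | (−120 − 100 + 60)/12 = −13.3 | −22.0 | −15.0 |
| 4 | 0 | (−90 − 200)/10 = −29.0 | −29.0 | −15.0 |

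**Range** over p from −10 to −20, b from 40 to 60, s from 20 to 40 and r from 0 to 4. Under the has-reported reading, improvement is overstated as follows:

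- One new case: from 1 × (10 + 20)/11 = 2.7 to 1 × (36 + 40)/11 = 6.9 points.
- Two new cases: from 2 × 30/12 = 5.0 to 2 × 76/12 = 12.7 points.

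Under the visit-by-visit reading, with 0 to 2 new cases, the result runs from overstating improvement by 10.0 points (p = −20, s = 40, r = 0, n = 2: A = −10.0) to understating it by 20.0 (p = −10, b = 60, r = 4, n = 0: A = −30.0).

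**How likely.** With 5 of 15 free of tinnitus at baseline and an assumed onset rate of 5% to 20%, the chance of no new case is 0.95⁵ = 77% to 0.80⁵ = 33%. The chance of two or more is 2% to 26%.

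**The case against.** It is reasonable not to give a tinnitus-impact questionnaire to people without tinnitus, and change among those who had it before surgery is a coherent question. The plan tests no hypothesis and commits to no mean THI change. Every figure in points above rests on assumed inputs and on a benchmark that scores absence as zero. New-onset participants still complete the THI later, so their scores exist and could be shown. All of this stands, and it keeps the point small. It does not supply a preimplant value for those participants or say how they are summarised.

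A reader might infer three stronger things that the documents do not support.

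- *The harm signal is lost.* It is not. Section 12.1 lists increased tinnitus as an anticipated adverse event, adverse events are assessed at each postoperative test interval, and they are summarised by number and percent.
- *Participants whose tinnitus resolves also drop out.* That needs the visit-by-visit reading of section 8.3.3. The wording of section 9.0 more naturally keeps them in.
- *The plan excludes new-onset cases.* No sentence does so. Their absence follows from the missing preimplant score and the lack of any value for absence of tinnitus.

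The case report forms in Appendix A are not visible and may already record tinnitus status.

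**Conclusion.** The point holds for new-onset tinnitus under every reading of the rule: such a participant has a postoperative THI and no preimplant score, and cannot enter the comparison in the Synopsis. The omission leans the THI result towards benefit, judged against a comparison of everyone with tinnitus at either time in which absence counts as zero impact and baseline cases do not worsen on average by as much as the new-onset score. For resolved tinnitus the text is ambiguous rather than wrong.

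The size cannot be stated from the documents. It is zero under the has-reported reading if no new-onset case occurs, and the illustrated values show scale only. The effect is confined to one secondary questionnaire in a descriptive feasibility study. The change is optional.

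**What to change.** - At baseline, 3, 6 and 12 months, record tinnitus as present or absent for every participant.
- State in section 8.3.3 that anyone who has ever reported tinnitus stays in the comparison, and that a visit with no tinnitus counts as zero impact.
- In section 11.0, item 6, write: *THI at 12 months will be compared with preimplant in all participants with tinnitus at either time, and also in those with tinnitus at baseline. Individual and group comparisons will be conducted. Persistent, resolved and new-onset cases will be reported separately.*
- List each participant's THI by visit beside any tinnitus adverse event.

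The cost is one yes/no question per visit, a few sentences and one listing. Participants who never have tinnitus complete no extra questionnaire. The drawback is that scoring absence as zero mixes the presence of tinnitus with its impact, which is why the three groups and the change in those with baseline tinnitus should appear alongside the combined figure.
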